## 9.4. Data Sources

In the C4591036 study, the Site Investigator has ultimate responsibility for the collection and reporting of all clinical, safety, and laboratory data entered on the CRFs and any other data collection forms (source documents) and ensuring that they are accurate, authentic/original,

attributable, complete, consistent, legible, timely (contemporaneous), enduring, and available when required. Any corrections to entries made in the CRFs or source documents must be dated, initialed, and explained (if necessary) and should not obscure the original entry. In most cases the source documents are the hospital or the physician's chart. In these cases, data collected on the CRFs must match those charts. In rare cases, the CRF may also serve as the source document.

All data derived from the medical records will be de-identified and coded. Pfizer will only receive de-identified and aggregated data results.

## 9.5. Study Size

The study cohort for this interim analysis will be comprised of the interim study data collected for the first 300^2 participants enrolled in C4591036 between 21 Nov 2022 and 15 Apr 2025 who meet study inclusion/exclusion criteria, from acute presentation to the 1-year post-discharge study visit. Enrollment per participant cohort is as follows:

- 200 prospectively and retrospectively ascertained cases of children, adolescents, and young adults <21 years of age who receive care at participating medical centers for myocarditis/pericarditis associated with COMIRNATY, and
- 100 persons <21 years of age with COVID-associated myocarditis/pericarditis, including MIS-C.

As the statistical analysis is descriptive in nature, the study sample size is not based on any statistical hypothesis testing.

Study participants' medical history, clinical course, long-term sequelae, risk factors, time to resolution and impact on quality of life associated with myocarditis/pericarditis associated with COMIRNATY will be characterized and summarized using descriptive statistics. These summaries will encompass the safety measurements and assessments, as well as the primary composite study endpoint. Similar summaries will be produced for the comparator cohort of children and young adults <21 years old with myocarditis/pericarditis associated with COVID-19, including MIS-C.

The study cohort may be updated and planned analyses repeated to allow for the evaluation of additional annual study visits as those milestones are met.

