### Data analysis:

Study participants' medical history, clinical course, long-term sequelae (see Table 1), risk factors for long term sequelae, time to resolution, and quality of life impact of myocarditis/pericarditis associated with COMIRNATY will be characterized and summarized using descriptive statistics (see Section 9.7) at the study time points, namely during the hospitalization, at 2 weeks, 6 weeks, and 6 months, and annually up to the 1-year post-discharge study visit. Similar summaries will be produced for a comparator cohort of children and young adults <21 years of age with COVID-19–associated myocarditis/pericarditis, including MIS-C.

Detailed methodology for the statistical analysis of the study data, in alignment with the objectives outlined in Section 8, will be documented in a statistical analysis plan (SAP), which will be dated, filed, and maintained by the sponsor.

**Milestones**: Data will be accessed for this study after institutional review board approval is received, and data cleaning activities have been completed. The following planned milestones are shown below.

Start of data collection: 01 Sep 2025 End of data collection: 31 Dec 2025

Submission of interim study report to FDA: 31 Mar 2026

<sup>1 200 prospectively ascertained or retrospective ascertained cases of COMIRNATY associated myocarditis or pericarditis and 100 cases of COVID-19 associated myocarditis or pericarditis are the minimum enrollment targets in the C4591036 study.

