### 9.2. Setting

This study analyzes data from the ongoing C4591036 study, "Low- interventional Study of Myocarditis and Pericarditis Associated with COMIRNATY in Persons Less Than 21 Years of Age."

Three cohorts of participants are included in this study:

**Cohort 1**: Prospectively ascertained cases of probable or confirmed myocarditis/pericarditis associated with COMIRNATY, i.e., participants enrolled under the protocol during hospitalization or ≤2 weeks after hospital discharge.

**Cohort 2**: Retrospectively ascertained cases of probable or confirmed myocarditis/pericarditis associated with COMIRNATY, i.e., participants enrolled >2 weeks after hospital discharge (combination of retrospective data collection from EMRs and prospective data from the time that the participant signs informed consent/assent). Participants can be retrospectively or prospectively ascertained and enrolled at any time from their COMIRNATY-associated myocarditis/pericarditis.

**Cohort 3**: Comparator cohort of COVID-19-related myocarditis/pericarditis, including MIS-C. Participants can be retrospectively or prospectively ascertained and enrolled at any time from their COVID-19 or MIS-C-associated myocarditis/pericarditis. Cohort 3 participants will not be separated into COVID-19-associated myocarditis/pericarditis with or without MIS-C because of the rarity of myocardial involvement in children with acute severe COVID-19.

Among Cohorts 2 and 3, a waiver of consent can be requested for collection of information related to clinical care when participants with a history of vaccine myocarditis/pericarditis or COVID-19-related myocarditis/pericarditis, including MIS-C, are unreachable after 5 documented contact attempts. Patients who are enrolled under a waiver will not undergo

any studies for research purposes. In such patients, data collection will be limited to "retrospective" medical records review, including images obtained in the course of clinical care. No activities that are solely research-related are obtained or required in waiver of consent participants.

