Study participants' medical history, clinical course, long-term sequelae, risk factors, time to resolution, and quality of life impact of myocarditis/pericarditis associated with COMIRNATY will be characterized and summarized using descriptive statistics at the study time points, namely during the hospitalization, at 2 weeks, 6 weeks, and 6 months, and annually up to 5 years of follow-up after illness onset. Similar summaries will be produced for a comparator cohort of children and young adults <21 years of age with COVID-19–associated myocarditis/pericarditis, including MIS-C.

Participant adherence to the C4591036 study design is required, including those activities specified in the SoA, at time points after enrollment. Relevant data will be collected from testing obtained as part of routine care prior to enrollment. The Schedule of Activities for C4591036 is in Table 2 below.

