- d. Because the primary study endpoint occurs at the 6-month visit, the 6-month window extends up to 1 year to maximize data capture. A single visit occurring within the 6-month window will always be analyzed with the 6-month endpoint. If there is more than 1 visit in the 6-month window, choose the visit closest to 6 months. However, for patients who have a 6-month visit, an additional visit between 9 months to up to 1 year can qualify for the 1-year visit window.
- e. The annual visits will have a window of 6 months before and after the year begins, with the exception of the 1-year visit. If there is more than 1 visit within an annual window, choose the visit closest to the year mark. For the 1-year visit, the window can begin at 9 months (39 weeks) from illness in patients who have a 6-month visit.
- f. Medical history will include complete cardiac and non-cardiac systems review. Medical history in the interim since the latest research evaluation will be obtained at each study visit.
- g. For patients with isolated pericarditis, echocardiograms will no longer be required as part of the research protocol once there is ≤ small pericardial effusion by echo and symptoms have resolved off medication.
- h. Echocardiogram at discharge is not required for the research protocol in participants who had LVEF ≥55% at baseline/Visit 1. However, we will collect data on echocardiograms obtained at the time of, or near, discharge in those participants who had them performed for clinical reasons.
- i. Echocardiograms at 6 months and annually between years 1 and 5 are not required for the research protocol in participants who have previously had 2 consecutive normal echocardiograms. However, data from such echocardiograms will be collected if conducted as part of clinical care.
- j. ECGs are not needed beyond the 6-month visit if there are no ECG abnormalities other than sinus bradycardia, sinus tachycardia, ectopic atrial rhythm, incomplete right bundle branch block and borderline right axis deviation (QRS axis less 100°) on two consecutive ECGs. As with other tests, if ECG is done for clinical purposes, it should be transmitted to the Core Lab.

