#### 9.9. Limitations of the Research Methods

As C4591079 utilizes data from C4591036, potential limitations are common to both studies and should be noted:

- Because of the decline in number of COMIRNATY-associated myocarditis cases (according to the Vaccines Adverse Events Reporting System [VAERS], cases reported in the US reached a peak in June 2021 and dropped dramatically after October 2021), the myocarditis/pericarditis cohort is largely comprised of retrospectively ascertained cases.
- Patients will be excluded from participation if plausible etiologies for myocarditis other than COMIRNATY-associated myocarditis are known at enrollment. It is possible that a plausible alternative etiology will be discovered only after a participant is enrolled. If so, those participants will be followed per C4591036 but will be accounted for separately in the statistical analysis.
- Some individuals who had COMIRNATY-associated myocarditis/pericarditis
  prior to the start of the study period may decline consent/assent or be difficult to
  reach. Each clinical center enrolling under C4591036 will work closely with
  pediatric offices to maximize return for scheduled visits. Participants who have
  returned to normal health and cardiac status may also be less inclined to return
  for follow-up at the recommended time points.
- A waiver of consent can be requested for collection of information related to clinical care when clinical sites are unable to reach participants with a history of vaccine myocarditis/pericarditis or COVID-19-related myocarditis/pericarditis, including MIS-C. In such patients, data collection will be limited to "retrospective" medical records review, including images obtained in the course of clinical care. No activities that are solely research-related are obtained or required.
- CMRIs are performed only when ordered as part of routine clinical care, and there may be practice variation among centers/providers regarding timing and protocols for cMRI.
- The COMIRNATY myocarditis and comparison participants are symptomatic
  patients evaluated and diagnosed in medical centers. They will not include
  individuals in the community with subclinical myocarditis/pericarditis. The study
  population will only include those with clinical myocarditis/pericarditis. Therefore,
  results from this study cannot be generalized to those in a subclinical
  myocarditis population.

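### The interim's horizon is 1 year in some sections and 5 years in another; cases discharged by about 21 Nov 2021 could have no protocol 6-month visit, and a 1-year stop omits most of their on-study visits

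*Protocol*

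**What the plan says.** **Horizon.** Section 9.5 defines the interim data as those of participants enrolled "between 21 Nov 2022 and 15 Apr 2025 who meet study inclusion/exclusion criteria, from acute presentation to the 1-year post-discharge study visit". The abstract (Study size, Data analysis) gives the same 1-year stop. Section 9.2, in a sentence that otherwise matches the abstract's, describes summaries "annually up to 5 years of follow-up after illness onset".

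**Windows.** In Table 2, visits date from discharge after the first hospitalization. The 6-month visit runs from 9 weeks to less than 1 year, and footnote d explains that "the 6-month window extends up to 1 year to maximize data capture" because the primary endpoint sits there. The annual visits have a window of 6 months either side.

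**Who is enrolled.** Section 9.9 reports that vaccine-associated "cases reported in the US reached a peak in June 2021 and dropped dramatically after October 2021" and that, as a result, "the myocarditis/pericarditis cohort is largely comprised of retrospectively ascertained cases". Cohort 2 data are a "combination of retrospective data collection from EMRs and prospective data from the time that the participant signs informed consent/assent". Before enrolment, only routine-care testing is available. Participants under a waiver of consent contribute records only.

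**Timetable.** The abstract gives: "Start of data collection: 01 Sep 2025 End of data collection: 31 Dec 2025". Sections 4 and 9.5 allow the analyses to be repeated for later annual visits, without a date or a commitment.

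**The concern.** The primary objective is long-term sequelae, and the rationale stresses standardized assessment read by core laboratories. Enrolment began more than a year after the reporting peak that supplied many of the vaccine cases. For a case from that peak, the visit carrying the primary endpoint had passed before the participant could join, while the visits attended on study fall mostly in year 2 and later.

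Two things are at stake. First, the two horizons give different analysis sets, and the 1-year one drops most of the long-term visits these participants could provide. Second, a single 6-month result pools participants whose tests the protocol required with participants whose tests depended on what a clinician ordered. Testing in routine care may follow symptoms or earlier abnormality, so the two groups need not give comparable frequencies.

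**Working it through.** No sample-size calculation is involved: the 300 is 200 + 100 and is stated not to rest on hypothesis testing. The check is calendar arithmetic.

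**Inputs**
- First enrolment date 21 Nov 2022; last 15 Apr 2025 (Section 9.5). That is 877 days, both ends counted.
- The 6-month window closes at discharge + 12 months, exclusive (Table 2).
- The 1-year window closes at discharge + 18 months (Table 2). Footnote e's exception for the 1-year visit is read as changing only the start.
- Reporting peak June 2021, steep fall after October 2021 (Section 9.9).
- Assumption: discharge falls in the month of the report.

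**Formulas.** Gap = 21 Nov 2022 − (discharge + 12 months). Lag = (discharge + 18 months) − 21 Nov 2022. Overlap = lag + 1 days, out of 877.

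| Discharge | 6-month window closes | Gap before enrolment opened | 1-year window closes | Lag after opening | Overlap with enrolment |
|---|---|---|---|---|---|
| 1 Jun 2021 | 1 Jun 2022 | 173 days | 1 Dec 2022 | 10 days | 11/877 = 1.3% |
| 30 Jun 2021 | 30 Jun 2022 | 144 days | 30 Dec 2022 | 39 days | 40/877 = 4.6% |
| 31 Oct 2021 | 31 Oct 2022 | 21 days | 30 Apr 2023 | 160 days | 161/877 = 18.4% |
| 22 Nov 2021 | 22 Nov 2022 | none (open 1 day) | 22 May 2023 | 182 days | 183/877 = 20.9% |

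**6-month visit.** Because the window is strictly under 1 year, a discharge on 21 Nov 2021 has its last window day on 20 Nov 2022. Every discharge up to that date is out of reach, which includes the whole June to October 2021 period. The 2-week and 6-week windows (ending at 3 and 9 weeks) closed earlier still. Table 4 gives participant report as the only source of patient-reported outcomes, so these could not be collected on study at any of the three visits.

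**1-year visit.** The share of participants enrolled before their 1-year window closed depends on the enrolment pattern, which the protocol does not give.
- Uniform enrolment: about 3% of June 2021 discharges, and about 10% of discharges spread evenly over June to October.
- Front-loaded enrolment with half-life h days, share = (1 − 2^(−t/h)) / (1 − 2^(−877/h)), where t is the overlap in days, averaged over discharge dates. For h = 365, 180 and 90: about 6%, 10% and 18% for June; 18%, 28% and 46% for June to October.

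**Later visits.** For discharges on 30 Jun and 31 Oct 2021, the 2-, 3- and 4-year marks fall in June and October of 2023, 2024 and 2025, all before 31 Dec 2025. At that date these participants are 4.5 and 4.2 years past discharge. A consenting participant therefore has at most one on-study annual visit inside a 1-year horizon and up to three outside it.

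**The case against.** The strongest reply is that a 1-year horizon is a legitimate scope for an interim report. The parent study follows participants to 5 years, repeat analyses are allowed for, and the ambidirectional design, the largely retrospective cohort and routine-care cMRI are all disclosed.

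The contrast between research and routine-care data is also narrower than it looks:
- cMRI is ordered only in routine care for everyone.
- LVEF at 6 months is presumed normal after values of at least 55% at 2 and 6 weeks.
- In years 1 to 5, echocardiogram, ECG and exercise testing fall away after normal results, and ambulatory monitoring is required only at 6 months. For a recovered 2021 case, a later visit may add little beyond history and patient-reported outcomes.
- Echo, ECG and cMRI outcomes come from core laboratories even when routine care ordered the test. The issue is who was tested, not how the images were read.

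All of this stands and limits the size of the point. It does not remove it. The disclosure in Section 9.9 does not say that the primary visit was unreachable on study for 2021 discharges. The repeat clause is optional and undated, although the 2- to 4-year marks for these cases will have passed by the end of data collection. Footnotes m and n of Table 2 offer optional research exercise and rhythm tests at annual visits to those who missed them at 6 months, and a 1-year stop leaves most such tests out for 2021 cases. The contradiction between Sections 4 and 9.5 and Section 9.2 is in the protocol itself and is not a detail deferred to the SAP. The layout of subgroup tables may properly sit in the SAP, which is not shown and may already provide it.

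**Conclusion.** The point holds in limited form. The horizon is contradictory and must be reconciled. On the protocol's own dates, no participant discharged on or before about 21 Nov 2021 could have a protocol 6-month visit, so the 6-month composite for these participants can come only from tests ordered in routine care. A 1-year stop leaves out most of their on-study visits.

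A reader might infer more than the documents support:
- *That most of the 200 vaccine cases are affected.* The peak is US national reporting, and no onset or discharge dates are given for the cohort. Cohort 2 starts at more than 2 weeks after discharge, so it can include later cases with ordinary protocol visits. Section 9.9 suggests a large share, but no number follows.
- *That none of their protocol-driven data is used.* The 1-year window closed 39 to 160 days after enrolment opened for discharges from 30 Jun to 31 Oct 2021, so early enrollees could have one on-study 1-year visit.
- *That very late enrollees distort the 1-year denominators.* The protocol states no denominator rule, and footnote e lets the 1-year window open at 39 weeks for those with a 6-month visit.

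The result rests on discharge dates close to reporting dates and on an 18-month end to the 1-year window. The abstract's enrolment end of 16 Apr 2025, against 15 Apr in Section 9.5, is clerical and changes nothing here.

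**What to change.** 1. In Sections 4 and 9.5, include the annual visits reached by the data cut, in line with Section 9.2, as supporting long-term summaries. Keep the 6-month composite as primary, and state that the longer horizon does not recover that endpoint for participants whose window closed before they could enrol.
2. Report the 6-month composite overall and in two groups: participants whose 6-month window was at least partly open after consent, and those whose window closed before consent or who were enrolled under a waiver (records only). State the number in each group.

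The cost is protocol and SAP wording and a few extra tables from data already collected in the parent study. The downside is smaller denominators in each group. The 15/16 April date can be aligned in the same edit.

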### 9.6. Data Management

An Electronic Data Capture (EDC) system is currently being used for ongoing collection of clinical, safety, and laboratory data under C4591036. The system is designed to support reliable and secure data entry for clinical research purposes and provides seamless integration of electronic case report forms (eCRFs), implementation of protocol amendments and Statistical Analysis System (SAS) and Extensible Markup Language (XML) study data exports. Data is entered directly from multiple study sites via a fully validated and 21 Code of Federal Regulations (CFR) Part 11 compliant, secure Web application and stored centrally. In addition, three central core laboratories are processing imaging data from echocardiography, cardiac MRI, and electrocardiography assessments performed on study participants.

<sup>2 200 prospectively ascertained or retrospective ascertained cases of COMIRNATY associated myocarditis or pericarditis and 100 cases of COVID-19 associated myocarditis or pericarditis are the minimum enrollment targets in the C4591036 study.

eCRFs are required for each included participant under C4591036. The completed original eCRFs are the sole property of Pfizer and should not be made available in any form to third parties, except for authorized representatives of Pfizer or appropriate regulatory authorities, without written permission from Pfizer.

For this study, EDC study data will be extracted and combined with imaging data for the study population defined in Section 9.5. All study data will be securely stored in a centralized repository, with adequate backup systems and access controls in place to protect against data loss and unauthorized access. Proper documentation and metadata will accompany the stored data to facilitate future retrieval and analysis in accordance with Carelon Research Standard Operating Procedures (SOPs).

## 9.7. Data Analysis

Detailed methodology for the summary and statistical analysis of the study data, in alignment with the objectives outlined in Section 8, will be documented in a statistical analysis plan (SAP), which will be dated, filed, and maintained by the sponsor. Descriptive statistics will include means, medians and standard deviations, first and third quartiles, minimum and maximum values for continuous variables, and absolute/relative frequencies for categorical data. Logistic regression will also be used to assess potential risk factors for binary outcomes. Mixed-effects linear regression models for repeated measures will be used to examine trends for continuous outcome measures. Other statistical measures will be described in the SAP.

All programming necessary for the creation of analytic datasets and the conduct and validation of statistical analyses outlined in the SAP will be performed using SAS.

## 9.8. Quality Control

The following quality control measures are in place for the ongoing C4591036 study, to ensure data quality and integrity:

- Integrated into the electronic data capture system: real time validations (including both inter- and intra-instrument data checks), inconsistent or questionable values flagged during entry, generation of an automatic edit report to the data entry client to provide the information necessary to investigate any data entry errors or resolved questions regarding out-of-range or questionable values, second level query tracking for real time access to unresolved queries as well as the date and time of query generation and resolution.
- Data review: ongoing data review of C4591036 data via manual listings and reports conducted by the clinical data manager and/or biostatistician; Pinnacle 21 validation of the data used in this interim analysis and any additional interim analyses in the future.
- Study-related monitoring activities: source data verification (SDV) through on-site and/or remote monitoring visits, Clinical Research Organization (CRO) and/or Sponsor audits, IRB/EC review, and regulatory agency inspections.
  - Source documents are filed at the investigator site. Investigators are required to maintain accurate and complete source documentation following the principles of ALCOA: Attributable, Legibility, Contemporaneous, Original, Accuracy.

In this study, all programming necessary for the extraction of study databases and creation of analytic datasets will adhere to Carelon Research programming standards and SOPs.

Data validation will take place consistently throughout the data management and analysis phases. Data quality checks will include independent programming of primary and key secondary results by a secondary statistician to verify findings, assessments of internal dataset consistency, and compliance checks against protocol criteria. All study databases and programming will be stored and archived in accordance with Carelon Research SOPs.

